^f The investigator will complete a separate angioedema attack CRF for each attack based upon their review of the data in the subject diary.

^g Serious Adverse Events (SAEs) are to be followed until 1-month post-treatment visit.

Note: Investigators will report all SAEs that occur ≤ 30 days after the last dose of investigational product and related SAEs that occur >30 days after the last dose of investigational product to Shire Pharmacovigilance Department.

Table 4 Blood Sample Collection for PK/PD Analyses

TREATMENT PERIOD 1	
Visit / Dose #	Blood Sampling Time Points^a
	C1 INH Antigen, C1 INH Functional, C4
1a / Dose 1 ^b	Predose 1 (within 15 min)
2a / Dose 2 ^c	Predose 2 (within 15 min)
8a / Dose 8	Predose 8 (within 15 min)
16a / Dose 16	Predose 16 (within 15 min)
24a / Dose 24	Predose 24 (within 15 min)
Either 27a or 28a / Dose 27 or 28 ^d	Predose 27 or 28 (within 15 min)
	48 hours postdose 27 or 28 (±3 hours)
TREATMENT PERIOD 2	
1b / Dose 1	Predose 1 (within 15 min)
2b / Dose 2 ^c	Predose 2 (within 15 min)
8b / Dose 8	Predose 8 (within 15 min)
16b / Dose 16	Predose 16 (within 15 min)
24b / Dose 24	Predose 24 (within 15 min)
28b / Dose 28	Predose 28 (within 15 min)
	24 hours postdose 28 (±3 hours) – optional sampling time point
	48 hours postdose 28 (±3 hours)
	72 hours postdose 28 (±6 hours) – optional sampling time point
	96 hours postdose 28 (±6 hours)
EARLY DISCONTINUATION (if applicable) and POST-TREATMENT	
Early discontinuation	
1-week (± 1 day)	
1-month (± 2 days)	

C1 INH=C1 inhibitor; PD=pharmacodynamics; PK=pharmacokinetics

^a The actual date and time of each sample collection will be recorded, therefore the sampling window is provided for guidance is as an approximate value.

^b C1q concentration will also be assessed using the baseline sample (predose at Dosing Visit 1a).

^c Subjects who self-administer investigational product without supervision are not required to have a blood sample collected at Visit 2a or 2b.

^d To avoid collecting a PK/PD blood sample during the weekend, subjects have the option for a predose and 48 h postdose sample to be collected at either Visit 27a or 28a.

Note: Blood samples collected from subjects for PD assessments may also be used for exploratory HAE biomarker assays.

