Individual participation from the screening visit through the 1-month post-treatment visit will be approximately 9 months.

- Planned duration of screening period: Up to 21 days
- Planned duration of enrollment period: 6 months
- Planned duration of treatment period: Treatment Periods 1 and 2 are 14 weeks each (total 28 weeks) with no washout between periods
- Planned duration of follow-up: 1 month follow-up in total, with safety assessments at both 1-week and 1-month post-treatment

Endpoints and statistical analysis:

Primary Efficacy Endpoint: The NNA recorded during each treatment period. The NNA is computed as the number of attacks per month (ie, 30.4 days) of exposure (NNA = 30.4 x [number of attacks during treatment period]/[days of treatment period]). If a subject discontinues during the treatment period, the denominator of the NNA will be the days on treatment for that subject; this is equivalent to the last observation carried forward imputation method to impute the missing information following the subject's discontinuation.

The primary analysis of the primary efficacy endpoint will test against the null hypothesis that the NNA of C1 esterase inhibitor [human] liquid for injection is greater than or equal to the NNA of placebo ($H_0: \mu_{C1\ INH} - \mu_{placebo} \geq 0$; $H_1: \mu_{C1\ INH} - \mu_{placebo} < 0$). The primary efficacy endpoint will be analyzed by using a linear mixed effect model with period, sequence, stratification factor (use of prophylactic therapy with C1 INH), and treatment as fixed effects, and subject nested within sequence as a random effect. The mean treatment difference ($\mu_{C1\ INH} - \mu_{placebo}$) will be estimated with a 95% confidence interval (CI).

To control the overall type 1 error, the primary and key secondary endpoints will be tested at the 0.05 significance level in the pre-specified order of the primary endpoint, key secondary endpoint 1, key secondary endpoint 2, and key secondary endpoint 3. Once one hypothesis test is not significant, the significance of all subsequent tests will not be assessed.

Key Secondary Efficacy Endpoints:

1. The proportion of subjects meeting the criterion of at least a 50% reduction in the NNA during the 2000 IU C1 esterase inhibitor [human] liquid for injection treatment period relative to the placebo period.
2. The NNA excluding the first 2 weeks of each treatment period.

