3. The proportion of subjects meeting the criterion of at least a 50% reduction in the NNA for the 2000 IU C1 esterase inhibitor [human] liquid for injection treatment period relative to the placebo period excluding the first 2 weeks of each treatment period.

Key secondary endpoints 1 and 3 are defined as achieving a $\geq 50\%$ reduction in the NNA (P_R) during the 2000 IU C1 esterase inhibitor [human] liquid for injection treatment period relative to the placebo period. Key secondary endpoints 1 and 3 will be analyzed as the proportion of subjects meeting criterion P_R . The null hypothesis is that P_R is less than or equal to 0.2 and the alternative hypothesis is that P_R is greater than 0.2. The proportion meeting criterion P_R will be estimated with an exact 95% CI. The lower limit of the 95% CI for the proportion will be compared with 0.2.

Analysis of key secondary endpoint 2 will follow the same method (ie, the linear mixed effect model) used for the primary efficacy endpoint.

Other Secondary Efficacy Endpoints:

- To determine the proportions of subjects achieving at least a 50% reduction in the NNA during a treatment period relative to the pretreatment assessment.
- Cumulative attack severity. This score is the sum of the maximum symptom severity recorded for each angioedema attack in a treatment period.
- Cumulative daily severity. This score is the sum of the severity scores recorded for every day of reported symptoms in a treatment period.
- Number of attack-free days during a treatment period.
- Number of angioedema attacks requiring acute treatment during a treatment period.
- Disease activity as measured by the 98-day AAS. This score is the sum of the daily AAS during a treatment period, where the daily AAS is the sum of AAS items per day.
- Results of the Angioedema Quality of Life (AE-QoL) questionnaire.
- Determine the response to icatibant when administered as treatment for an acute angioedema attack by:
 - Time to subject-assessed initial symptom improvement (TISI).
 - Time to subject-assessed complete symptom resolution (TCSR).

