Subjects in the Full Analysis Set (Section 9.7) will be used to evaluate the efficacy of SC administration of C1 esterase inhibitor [human] liquid for injection. The treatment differences in clinical responder rate, both of which are defined within treatments, will be analyzed using McNemar's test for testing equality of proportions of responders within treatments. All other secondary endpoints will be analyzed using a linear mixed effect model with period, sequence, stratification factor (use of prophylactic therapy with C1 INH), and treatment as fixed effects, and subject nested within sequence as a random effect. The results of all secondary efficacy

analyses will be summarized by the point estimate of within-subject treatment differences or response rates and the corresponding 95% CI. Descriptive statistics (n, median, 25% and 75% quartiles, and range) will be provided to summarize icatibant-related efficacy endpoints (TISI and TCSR) by treatment and icatibant-treated angioedema attack for all subjects in the Full Analysis Set. Where appropriate (for subjects ≥ 12 to < 18 years of age) other rescue medications used to treat acute angioedema attacks will also be summarized using descriptive statistics. In addition, angioedema attacks will be summarized by the maximum symptom severity and treatment for all subjects in the Full Analysis Set.

Safety Endpoints:

- Number of subjects experiencing AEs, including severity and causality. AEs will also be assessed by time of onset (eg, during administration of investigational product or within 24 hours after the end of injection of investigational product).
- Clinical laboratory tests (hematology, chemistry, and coagulation), vital signs, and ECG findings will be summarized by treatment and visit. Potentially clinically important findings will also be summarized or listed.
- Incidence, severity (mild, moderate, severe), overall impact on daily living, and duration of SC injection site reactions.
- Results of C1 INH antibody testing will be reported for individual subjects and summarized.
- Tolerability of icatibant therapy for acute angioedema attacks will be summarized.

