6.3 Allocation of Subjects to Treatment Sequence

This is a double-blind, placebo-controlled, 2-period, 3-sequence, partial crossover study. At least 66 eligible subjects will be randomized to 1 of 3 treatment sequences (Table 7) prior to the first dose of investigational product in Treatment Period 1. The actual treatment sequence given to individual subjects is determined by a randomization schedule automatically assigned by the IRT.

Table 7 Treatment Sequences

Sequence	Treatment: Period 1/Period 2	Approximate Number of Subjects Randomized
1	A/B	26
2	B/A	26
3	A/A	14

Treatment A=2000 IU (4.0 mL) C1 esterase inhibitor [human] liquid for injection administered SC twice weekly (every 3 or 4 days) for 14 weeks.

Treatment B=Placebo (4.0 mL) administered SC twice weekly (every 3 or 4 days) for 14 weeks.

Subject numbers are assigned to all subjects as they consent to take part in the study. Within each level of use of prophylactic therapy with C1 INH across sites, the subject number is assigned to subjects according to the sequence of presentation for study participation. Subject number is unique within a protocol.

The randomization number represents a unique number corresponding to treatment sequence allocated to the subject, once eligibility has been determined. A randomization number will be assigned by the IRT at the baseline visit (predose Visit 1a) after subject eligibility has been confirmed using the randomization criteria. The randomization schedule will be stratified for use of prophylactic therapy with C1 INH at the time of enrollment versus no prophylactic therapy with C1 INH at the time of enrollment. Subjects will be randomized to the treatment sequence 1 (A/B), 2 (B/A), or 3 (A/A) in the randomization ratio of 2:2:1.

The subject's treatment sequence will be held in strict confidence. The treatment sequence for an individual subject may be broken in cases of emergency or for reasons of subject safety, as described in Section 6.4.1.

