Subjects in the Full Analysis Set (Section 9.7) that are randomized to Treatment Sequence 1 (A/B) or 2 (B/A) will be used to assess the secondary efficacy endpoints in the evaluation of the efficacy of SC administration of C1 esterase inhibitor [human] liquid for injection compared to placebo. The treatment differences in clinical responder rate, both of which are defined within treatments, will be analyzed using McNemar's test for testing equality of proportions of responders within treatments. All other secondary endpoints will be analyzed using a linear mixed effect model with period, sequence, stratification factor (use of prophylactic therapy with C1 INH), and treatment as fixed effects, and subject nested within sequence as a random effect. The results of all secondary efficacy analyses will be summarized by the point estimate of within-subject treatment differences or response rates and the corresponding 95% CI. Descriptive statistics (n, median, 25% and 75% quartiles, and range) will be provided to summarize icatibant-related efficacy endpoints (TISI and TCSR) by treatment and icatibant-treated angioedema attack for all subjects in the Full Analysis Set. Where appropriate (for subjects ≥ 12 to < 18 years of age), other rescue medications used to treat acute angioedema attacks will also be summarized using descriptive statistics. In addition, angioedema attacks will be summarized by the maximum symptom severity and treatment for all subjects in the Full Analysis Set.

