- Kaplan-Meier estimate of time to initial improvement and time to complete resolution since onset of attack by attack order during the treatment period.

The treatment differences in clinical responder rates, both of which are defined within treatments, i.e., the difference in the proportions of subjects with a clinical response to C1 INH

or placebo, each of them will be analyzed using McNemar's test for testing equality of proportions of responders within treatments.

Cumulative attack severity, cumulative daily severity, number of attack-free days during a treatment period and the 98-day AAS will be analyzed using a linear mixed effect model with period, sequence, use of prophylactic therapy with C1 INH, which is derived by long-term prevention with C1 INH at randomization, and treatment as fixed effects, and subject nested within sequence as a random effect. If the variance-covariance matrix of random effects is not positive definite, a mixed effect model with the same fixed effects and subject nested within sequence as repeated measurements will be performed instead. The results will be summarized by the point estimate of within-subject treatment differences or response rates and the corresponding 95% CI.

Kaplan-Meier analysis will be performed on all subjects in the Full Analysis Set without censoring. Median, 25%, 75% quartiles and their CI's will be estimated for time to initial improvement / complete resoluction since acute treatment administration / onset of attack.

Summary statistics (n, mean, SD, median, minimum and maximum) will be provided on each dimension and total score of AE-QoL by treatment and visit. A table will be provided summarizing the change from baseline to each visit and the last observation recorded within the treatment period for a subject's response to each dimension and the total score of AE-QoL.

In addition, angioedema attacks will be summarized by the maximum symptom severity of the attack and treatment for all subjects in the Full Analysis Set. Acute angioedema attacks will be summarized by acute therapy, the maximum symptom severity of the attack and treatment for all subjects in the Full Analysis Set.

Cumulative attack severity, cumulative daily severity and number of attack-free days will be plotted by treatment for the subjects who are randomized to the first two treatment sequences (A/B or B/A) in the Full Analysis Set.

Details on derivation of normalized efficacy variables are provided in the Appendix.

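### The NNA responder rates are compared with McNemar's test, which ignores period and sequence: some power is lost if there is a period effect, and the estimate is biased if A/B and B/A give unequal numbers of pairs

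*Protocol*

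**What the plan says.** The responder measure is a secondary one outside the key set, and the plan words it as follows: "To determine the proportions of subjects achieving at least a 50% reduction in the NNA during a treatment period relative to the pretreatment assessment". SAP 10.4 widens it to reductions of 50%, 70%, 90% and 100% and to an NNA below 1. Each period yields its own yes/no response, so a crossover subject contributes one pair.

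The synopsis sets the test: "The treatment differences in clinical responder rate, both of which are defined within treatments, will be analyzed using McNemar's test". Protocol 9.8.2.2 repeats this, stating that the difference "will be analyzed using McNemar's test for testing equality of proportions of responders within treatments". SAP 10.4 says of the responder rates: "each of them will be analyzed using McNemar's test for testing equality of proportions of responders within treatments". None of the three adds a period or sequence term. The subjects used are those "that are randomized to Treatment Sequence 1 (A/B) or 2 (B/A) will be used to assess the secondary efficacy endpoints".

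The synopsis treats the remaining endpoints differently: "All other secondary endpoints will be analyzed using a linear mixed effect model with period, sequence, stratification factor". The primary analysis uses a "linear mixed effect model with period, sequence, stratification factor (use of prophylactic therapy with C1 INH), and treatment as fixed effects". HRQoL SAP 6.4.1 (Objective 3) analyses AE-QoL and AAS responders, which are also binary, with mixed logistic models containing period and sequence.

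I found no period-adjusted alternative for the NNA responder rates in the text available to me. The opening of SAP 10.5 was not part of that text.

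**The concern.** McNemar's test pools the A/B and B/A pairs and uses only whether a discordant pair favours active or placebo. If response tends to be better or worse in Period 2 whatever the treatment, that shift enters A/B pairs with one sign and B/A pairs with the other. With equal numbers of pairs it cancels in the estimate, but it still adds discordant pairs and so costs power. With unequal numbers it does not cancel, and part of the period effect is reported as treatment effect.

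Unequal numbers are possible. Allocation plans equal crossover groups ("Subjects will be randomized to the treatment sequence 1 (A/B), 2 (B/A), or 3 (A/A) in the randomization ratio of 2:2:1", about 26 each), but SAP 2.5 counts on 44 crossover completers and protocol 4.4 does not replace dropouts. A subject who stops in Period 2 keeps an NNA for both periods, because the denominator becomes days on treatment. One who stops in Period 1 has no observed Period 2 value and forms no pair. Placebo comes first in B/A, so that sequence may lose more pairs; this is an inference, and the plan gives no figure for it.

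The protocol also promises a point estimate and 95% CI for the secondary endpoints, so a reported estimate is affected as well as a p-value.

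**Working it through.** **Nearest stated figure.** The plan gives no power, response rates or period effect for this comparison. The closest figure is the primary one: 44 crossover subjects, difference 1.0, SD of the difference 2.0 (SAP 2.5), one-sided 0.025. The noncentrality is 1.0/(2.0/√44) = 3.32, and the noncentral t gives power 0.900, matching the stated 90%.

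**Bias formula.** Let π be the Period 2 minus Period 1 difference in response rate and τ the treatment difference. The active-minus-placebo difference has expectation τ − π in A/B and τ + π in B/A. McNemar's estimate averages over all N pairs:

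E(estimate) = τ + π × (n_BA − n_AB)/N

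With no treatment effect the bias is therefore π × (n_BA − n_AB)/N. It is zero if the pairs are equal or π = 0. Half the between-sequence difference in mean (Period 1 minus Period 2) response removes π at any split.

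**Assumed inputs (none in the documents).** Logistic response with a normal subject effect, SD 1.5 and intercept −0.5; period log-odds 0.5, 1.0 or −1.0 (an odds ratio of about 2.7 or its inverse). Averaged over subjects, placebo response is 41.2% in Period 1. In Period 2 it is 50.0%, 58.8% or 25.4%, so π = 8.8, 17.6 or −15.8 points.

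**Bias with no treatment effect:**
- 22/22: 0.
- 25/23: (−2/48) × 8.8 = −0.4 and (−2/48) × 17.6 = −0.7 points (0.3 and 0.7 in size by simulation).
- 25/19: (−6/44) × 17.6 = −2.4, or (−6/44) × (−15.8) = +2.2 points.
- 26/18: (−8/44) × 17.6 = −3.2, or (−8/44) × (−15.8) = +2.9 points.

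**Power by simulation**, treatment log-odds 1.2 (a true difference of about 20 points), two-sided 0.05:

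| Pairs A/B, B/A | Period log-odds | McNemar | Prescott |
|---|---|---|---|
| 22/22 | 0.5 | 62.0% | 62.5% |
| 22/22 | 1.0 | 57.5% | 60.2% |
| 25/23 | 0.5 | 64.5% | 66.1% |
| 25/23 | 1.0 | 58.6% | 64.0% |
| 25/19 | 1.0 | 47% | 60% |
| 26/18 | 1.0 | 44% | 60% |
| 25/19 | −1.0 | 68% | 60% |
| 26/18 | −1.0 | 71% | about 60% |

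In the last two rows McNemar's advantage is bias towards active and not real sensitivity. With no period effect the two tests differ by at most about 1 to 1.5 points.

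**Type I error.** At period log-odds of 1 in size, the chance of a false result favouring active is 1.0% or 3.7% at 25/19 and 0.8% or 4.3% at 26/18, depending on the direction of the period effect, against 2.5% nominal. The other tail moves the opposite way, so the two-sided total is about 4.7% and 5.1 to 5.3%. With equal pairs the test is conservative, falling from 4.8% to 2.5% as the period log-odds rises from 0 to 2. Prescott's test stays near nominal.

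**How extreme the splits are.** Period 2 dropouts still form pairs, so the pair count is 44 plus those dropouts. With 52 randomized to A/B and B/A, 25/19 needs all 8 planned non-completers to stop in Period 1, 7 of them in B/A. A 26/18 split needs all 8 to stop in B/A Period 1. If half stop in Period 1, split 3:1, the result is 25/23.

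**The case against.** The strongest reply is that little is likely to be lost. Allocation is equal by design, and the large power gaps need both a near-maximal imbalance and a period odds ratio with no source in the plan.

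The only period evidence in the documents points to a small effect. In protocol Table 6 (the Phase 2 crossover study) the dose difference in number of attacks was −0.72 in A/B and −0.48 in B/A. The implied period shift is (−0.72 + 0.48)/2 = −0.12 attacks per month, against an overall difference of −0.61, and no sequence effect was seen on any endpoint (p ≥ 0.6290). That evidence is limited: 22 completers, 8-week periods, and two active doses with no placebo.

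The endpoint also dichotomises NNA, which the primary model already compares with period and sequence adjustment. It lies outside the hierarchy in SAP 10.3, where trial success rests on the primary endpoint alone. And a period term does not remove the A/B carryover that protocol 9.8.1 discusses.

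All of this stands, and it limits the size of the point. It does not explain why this binary endpoint is left unadjusted while the HRQoL responders are adjusted, nor does it guarantee equal pairs.

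**Conclusion.** The point holds as an inexpensive improvement to a secondary analysis. McNemar's test is valid but somewhat inefficient with equal pairs. With unequal pairs its estimate is biased by the pair imbalance times the period difference, in a direction that cannot be known beforehand. Realistic sizes are a few power points at most near balance and under 1 point of bias at 25/23. The 44 to 47% against about 60% comparison, and the 2 to 3 points of bias, are near-worst cases. All sizes rest on the assumed subject SD, response rate, period effect and dropout split.

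A reader might infer more than the documents support:
- That any period effect lowers power. The loss is relative to a period-adjusted test. Under imbalance the bias can raise the rejection rate, and a period effect can also raise power by shifting response rates.
- That type I error is inflated. At period log-odds up to 1 the two-sided total stays near 5% and only the split between tails moves. It reaches 6.3% only at 26/18 with period log-odds up to 2.
- That B/A will lose more pairs. This is plausible, but no dropout split is given.
- That the trial's conclusion is at risk. The endpoint carries no weight in the testing hierarchy.

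**What to change.** In the synopsis, protocol 9.8.2.2 and SAP 10.4, make a period-adjusted analysis the main comparison of the NNA responder rates, using every A/B and B/A subject with a response in both periods:

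- Test: Prescott's test, which compares the within-subject score (Period 1 minus Period 2: −1, 0 or 1) between the two sequences.
- Estimate: half the between-sequence difference in the mean of that score, with its 95% CI.
- Acceptable alternative: a mixed logistic model with period and sequence, as in HRQoL SAP 6.4.1.
- Keep McNemar's test as a supportive analysis.

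A test using discordant pairs only (Mainland-Gart) is not a good substitute: it was no more powerful than McNemar's test in balanced settings with a sizeable period effect.

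The cost is wording in three places, a few lines of code, and at most about 1 to 1.5 points of power if there is no period effect. Carryover in A/B is not addressed by this change.
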